Quantitative rating scale based on preoperative prediction of lymph node dissection in patients with thyroid cancer

Research program

NCT ID: Not yet assigned

Date of document: 2023.10.29

Research program

I. Background of the study

The incidence of papillary thyroid carcinoma (PTC) has been on an elevated trend in recent years, and lymph node metastasis is present in 20%-50% of PTC patients. Usually, lymph node involvement in PTC patients is related to the recurrence of PTC after surgery, and 30% of patients recur without lymph node dissection, among which the risk of cervical central lymph node metastasis is the greatest, so it seems to be a good choice to perform lymph node dissection for patients after thyroidectomy, but in fact, there is a controversy at home and abroad as to whether to perform lymph node dissection or not. The 2021 Chinese Society of Clinical Oncology (CSCO) guidelines for the diagnosis and treatment of differentiated thyroid cancer state that prophylactic central lymph node dissection (PCND) may increase the incidence of postoperative complications, but due to the high metastatic rate of PTC and the ability of PCND to effectively prevent recurrence and reoperation, countries in the East Asian region perform prophylactic lymph node dissection on almost all patients with PTC. However, for more countries in Europe and the United States, performing PCND has become a non-essential, individualized option.

The aim of this study is to produce a new type of scoring scale by collecting multifactorial data from patients who have undergone previous thyroidectomy from 2021-2023, to individualize the scoring of patients based on

a variety of factors prior to surgery, to be able to more accurately predict whether a patient does have lymph node metastasis and whether prophylactic lymph node dissection is needed before surgery is performed, and to be able to avoid complications from surgery for patients who do not need dissection. For patients who do not need lymph node dissection, it can avoid complications caused by surgery, while for patients who do have lymph node metastasis, it can prevent the recurrence of their cancer. This will change the current situation in which it is impossible to accurately determine the actual situation through simple preoperative examination or to perform prophylactic lymph node dissection for all PTC patients.

II.Purpose of the study

To create a quantitative rating scale for preoperative prediction of the need for lymph node dissection in patients with thyroid cancer.

Objects of the study

1. Selection of research subjects

From 2021 to 2023, 500 patients with previous papillary thyroid cancer surgery were selected in the Second Affiliated Hospital of Xi'an Jiaotong University for the production of quantitative scoring scales, as well as 300 patients with subsequent new admissions of papillary thyroid cancer for validation.

Inclusion criteria: (1) Age 16-80 years old;

(2) Patients with papillary thyroid cancer;

(3) Consciousness and ability to communicate normally.

Exclusion criteria: (1) Preoperative puncture pathology suggests that there are other types of tumors, such as medullary carcinoma or undifferentiated carcinoma;

(2) Age less than 16 years old.

Exclusion criteria: (1) Postoperative pathology suggests that there are other types of tumors, such as medullary carcinoma or undifferentiated carcinoma.

IV. Observation indicators

Basic information of patients: gender, age, height, weight, BMI and whether lymph node dissection was performed during previous surgery;

Tumor primary foci: unilateral/bilateral tumor, tumor diameter size, tumor focality, tumor invasion, and cases suggesting lymph node metastasis;

Preoperative ultrasonographic manifestations: cystic solidity of the tumor, echo intensity, whether the border is clear, whether there is calcification, aspect ratio, and whether there are enlarged lymph nodes in the neck;

Preoperative laboratory tests: TSH, TPOAb, TgAb, and blood calcium;

Genetic test results: TERT gene polymorphism (C250T), TERT gene polymorphism (C228T), NRAS gene polymorphism (Q61R), B-raf gene mutation.

The above data were collected from the medical records of previous patients to create a quantitative rating scale, and then new patients were evaluated using the scale and the above data information was collected from the new patients for comparison and validation.

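### The title, aim and purpose name three different prediction targets, and no recorded item measures the need for dissection; the data can support at most a conclusion about node metastasis in papillary thyroid cancer

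*Protocol*

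**What the plan says.** The Protocol states what the scale predicts in three places, each time differently.

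- Title: "Quantitative rating scale based on preoperative prediction of lymph node dissection in patients with thyroid cancer". The target is dissection.
- Section I, aim: "whether a patient does have lymph node metastasis and whether prophylactic lymph node dissection is needed before surgery is performed". There are two targets, metastasis and need. The same sentence adds "to be able to avoid complications from surgery for patients who do not need dissection".
- Section II, the formal purpose: "To create a quantitative rating scale for preoperative prediction of the need for lymph node dissection in patients with thyroid cancer". The target is need alone.

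The aim paragraph goes on to expected benefits: "For patients who do not need lymph node dissection, it can avoid complications caused by surgery", and "for patients who do have lymph node metastasis, it can prevent the recurrence of their cancer".

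Under the objects of the study, the development cohort is described as "500 patients with previous papillary thyroid cancer surgery were selected"; another 300 newly admitted papillary patients form the validation cohort. Section IV lists the data items. Its closing paragraph says that these items, taken from past records, are used to create the scale and that the same items are collected from new patients to validate it.

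**The concern.** A prediction scale is defined by its outcome. Here the outcome changes between title, aim and purpose, and the version in the formal purpose is a judgement that nothing in the data set records.

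Two things could go wrong if the document is followed literally. A team working from the title could take dissection performed as the outcome, and the scale would then learn what surgeons used to do. Alternatively, a team could fit the scale to node metastasis and report it, in the words of Section II, as showing who needs dissection. Neither result answers the question in Section II, and the second could be read as evidence about which patients can forgo dissection.

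**Working it through.** No power or sample-size formula applies, and the Protocol gives no figure to reproduce on this point. The check is a count of the Section IV items and a comparison of each candidate outcome with the stated target.

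**Step 1: count the items in Section IV.**

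| Group | Items | Number |
|---|---|---|
| Basic information | sex, age, height, weight, BMI, dissection at the earlier operation | 6 |
| Primary tumor | laterality, size, focality, invasion, node-metastasis item | 5 |
| Ultrasound | five features of the tumor, enlarged neck nodes | 6 |
| Laboratory | TSH, two antibodies, calcium | 4 |
| Genetic | two TERT variants, NRAS, B-raf | 4 |

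6 + 5 + 6 + 4 + 4 = 25. Counting the two TERT variants as one gives 24 and changes nothing below.

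**Step 2: look for an item that measures need.** Such an item would be a stated criterion for need, or an outcome that weighs the benefit of dissection against its harm. There are 0 of 25. Two items come near, which leaves 25 − 2 = 23 descriptors of patient, tumor, imaging, laboratory or genetic status. (The Protocol assigns no roles to its items; this grouping is mine.)

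**Step 3: test the two near items.**

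- *Dissection performed.* This is a past treatment decision. The Background says that "countries in the East Asian region perform prophylactic lymph node dissection on almost all patients with PTC", and the study exists because that practice may be broader than necessary. An item that records the practice in question cannot define who needs it.
- *The node-metastasis item.* This is disease status. It stands under the primary-tumor group, with no statement whether it comes from pathology or imaging. No sentence says that it stands for need, and the aim joins the two with 'and'.

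**Step 4: how far apart can the two near items be?** The Background gives a metastasis rate of 20%-50% in papillary cancer. The site's dissection rate is not given. As an illustration, assume the limiting case in which all 500 development patients were dissected and the Background range applies to them. Dissected patients without metastasis would then number between 500 × (1 − 0.50) = 250 and 500 × (1 − 0.20) = 400. In that case the two targets disagree for half to four fifths of the cohort, and dissection performed would not vary at all, so no scale could be fitted to it. The true figures depend on the site's rate; the point does not rest on them.

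**Step 5: population.** The title and Section II say thyroid cancer. Both cohorts, 500 + 300 = 800, are papillary only, and other tumor types are excluded on preoperative and on postoperative pathology.

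**The case against.** The strongest reply is that metastasis is plainly meant as the basis for judging need. The aim puts metastasis first, and the sentence after it sets patients who do not need dissection against patients who do have metastasis. This is a natural reading and may well be the intention. On that reading the defect is an unstated proxy, which a clause could repair. But no sentence states the equivalence, and the Background describes the decision as a trade-off between complications and recurrence, which node status alone does not settle.

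Other parts of the reply stand and limit the point:

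- A reader might infer that the scale's performance is bound to be performance for node metastasis. The Protocol does not support that, because the outcome is not fixed; node metastasis is the most the data can support.
- A reader might infer that the study fails because complications and recurrence are not recorded. Section II promises neither, and a study that develops and validates a scale need not measure the benefit of using it. Those statements belong to the rationale.
- A reader might infer that the study population is unclear. It is not: eligibility is unambiguously papillary, and the thyroid-cancer wording is a minor edit.
- The node item is listed apart from the ultrasound group, which has its own neck-node item. That makes an imaging source less likely but does not settle it.
- Analysis-set rules often sit in a SAP, which is not shown here. The prediction target and the items collected, however, are fixed in this Protocol, and a SAP cannot analyse an outcome that is not collected.

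**Conclusion.** The concern holds in this form: three statements of the target disagree, none of the 25 recorded items measures need, and a conclusion about who needs dissection is beyond the data. The recorded items can support at most a conclusion about node metastasis in papillary thyroid cancer, and a scale fitted to past dissection would only describe surgeons' practice.

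This is a defect in what the study may conclude, not a numerical error, and it has no effect size. It affects both cohorts. The study remains feasible, so the change should be made but is not a reason to stop. The conclusion assumes that Section IV is the full list of data, as its closing paragraph indicates, and that no definition of need is given outside the Protocol.

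**What to change.** 1. Restate the title and Section II as developing and validating a preoperative scale for the probability of lymph node metastasis in papillary thyroid cancer. If metastasis is meant as the stand-in for need, say so there. The change from thyroid to papillary is a minor edit made at the same time.
2. Name node metastasis on postoperative pathology as the outcome in both cohorts, and state that neither dissection performed nor imaging findings serve as the outcome. Record the source of node status in Section IV; an imaging-based status would overlap with the ultrasound item on enlarged neck nodes, which is a candidate predictor.
3. Do not treat undissected patients as confirmed node-negative. Report their number and their Section IV characteristics.
4. Limit conclusions to node metastasis, and present avoided complications and prevented recurrence as untested rationale.

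The cost is a narrower claim, one extra field from existing records, and possibly fewer evaluable patients than 500 and 300. The loss cannot be computed because the dissection rate is not stated; if the regional practice described in the Background holds at the site, it would be small. If the analysis is limited to dissected patients, they are selected by the surgeon's decision, while the scale is meant for all patients before surgery. That should be stated as a limitation.

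### Are 23 candidate items too many for a scale built on 500 patients with 100 to 250 events?

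*Protocol*

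**What the plan says.** Under Objects of the study, item 1, the development set is given as "500 patients with previous papillary thyroid cancer surgery were selected", and the validation set as "300 patients with subsequent new admissions of papillary thyroid cancer for validation". No calculation supports either number. The only outcome rate in the protocol is in section I, where "lymph node metastasis is present in 20%-50% of PTC patients".

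Section IV, Observation indicators, groups the data to be collected:

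- First group, 6 items: "Basic information of patients: gender, age, height, weight, BMI", plus whether nodes were dissected at the earlier operation.
- Primary tumour, 5 items: "unilateral/bilateral tumor, tumor diameter size, tumor focality, tumor invasion, and cases suggesting lymph node metastasis".
- Ultrasound, 6 items: "cystic solidity of the tumor, echo intensity, whether the border is clear, whether there is calcification, aspect ratio", plus enlarged neck nodes.
- Laboratory, 4 items: TSH, TPOAb, TgAb and calcium.
- Genetics, 4 items: "TERT gene polymorphism (C250T), TERT gene polymorphism (C228T), NRAS gene polymorphism (Q61R), B-raf gene mutation".

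The section closes by saying that these data, taken from earlier patients' records, serve to build the scale, and that new patients are then scored and compared. It does not say that every item enters the scale. It mentions no regression model, variable selection or shrinkage.

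**The concern.** A prediction model that estimates many coefficients from few events fits noise as well as signal. In new patients its high risks are then too high and its low risks too low. Sections I and II intend the scale to inform whether nodes should be dissected, so understated low risks would matter.

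The protocol sets both sides of the ratio, 500 patients and a list of more than twenty items, and justifies neither. The list also looks unpruned: BMI is computed from height and weight, yet all three appear, and TERT takes two places. The 300-patient validation could reveal a poorly calibrated scale but could not repair it.

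**Working it through.** **Plan's own figure.** The protocol gives no formula, target precision or expected model strength for 500, so that number can be neither reproduced nor shown to be wrong.

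**Items.** 6 + 5 + 6 + 4 + 4 = 25. Removing the earlier dissection and the nodal metastasis item leaves 23.

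**Events.** 500 × 0.20 = 100 and 500 × 0.50 = 250, if nodal status is known in all 500. Per candidate: 100/23 = 4.3 and 250/23 = 10.9.

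**Patients needed to hold shrinkage to 10%.** The usual criterion is n = p / [(S − 1) ln(1 − R²cs/S)], with p = 23 and S = 0.90. R²cs is Nagelkerke R² times its maximum, 1 − exp{2[q ln q + (1 − q) ln(1 − q)]}, which is 0.632 at q = 0.20 and 0.750 at q = 0.50. The protocol gives no R², so a range is assumed, with one parameter per item. Solving the same equation for S at n = 500 gives the expected shrinkage factor.

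| Nagelkerke R² (assumed) | n needed, q = 0.20 | S at 500, q = 0.20 | n needed, q = 0.50 | S at 500, q = 0.50 |
|---|---|---|---|---|
| 0.15 | 2,065 | 0.69 | 1,723 | 0.73 |
| 0.30 | 972 | 0.82 | 800 | 0.85 |
| 0.40 | 697 | 0.87 | 568 | 0.89 |
| 0.50 | 532 | 0.90 | 427 | 0.91 |

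Worked example, q = 0.20 and R² 0.30: R²cs = 0.30 × 0.632 = 0.190; ln(1 − 0.190/0.9) = −0.237; n = 23/(0.1 × 0.237), about 972.

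**Simulation of the worst method.** An unpenalised logistic model with 23 independent predictors, 8 of them real, was fitted to 500 patients (150 replicates per setting). For true AUC of about 0.68, 0.76 and 0.84, the mean calibration slope in new patients was 0.56, 0.72 and 0.75 at 20% prevalence, and 0.61, 0.78 and 0.80 at 50%. These are less favourable than the closed-form values.

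**Redundancy.** Under assumed adult distributions, BMI regressed on height and weight has R² of about 0.99, so the three are nearly but not exactly collinear. Modelling BMI alone takes p from 23 to 21; at q = 0.20 and R² 0.30, S moves from 0.82 to 0.84.

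**A shorter list.** One remedy would cap the model at 10 to 12 parameters. The number that 500 patients support at S = 0.90 is 500 × 0.1 × [−ln(1 − R²cs/0.9)]: 5.6 (q = 0.20, R² 0.15), 11.8 (0.20, 0.30), 6.7 (0.50, 0.15) and 14.4 (0.50, 0.30). The cap exceeds what is supported in both weak-predictor settings. In a simulation with 6 real predictors and true AUC of 0.70-0.71, going from 23 items to 10 raised the slope from 0.59-0.71 to 0.81-0.85, but new-patient AUC only from 0.67-0.68 to about 0.69.

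**The case for a change.** The strongest case for acting is that calling the items candidates does not remove the problem, because candidates count whenever selection uses the same outcomes. In a simulation with 6 real predictors and true AUC of 0.70, univariable screening and backward elimination kept only about 6 to 7 items, yet the slope was still 0.74 at 20% prevalence and 0.82-0.83 at 35%-50%. The SAP would inherit both the 500 patients and the list. Multi-level items such as echo intensity, and patients whose nodes were never dissected, would lower the ratio further. Section I itself doubts that simple preoperative examination is accurate, so strong predictors cannot be taken for granted.

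This stands as a warning about method. It does not show that the protocol states something wrong. What protects against the problem is reducing candidates without looking at the outcome, or penalised estimation. Either can be adopted with the same 500 patients and the same list, and the protocol rules out neither. Collecting an item does not commit anyone to modelling it: the list already contains the outcome and a description of the earlier operation. Height and weight must be recorded to obtain BMI, and both TERT variants must be recorded before they could be combined.

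**Conclusion.** No change to the protocol follows. The arithmetic holds: about 23 candidates, 100 to 250 events, and 427 to 2,065 patients needed for 10% shrinkage, depending on the assumed prevalence and R². At 500 the shortfall is serious if predictors are weak and events are near 100, and small or absent by the closed-form criterion if predictors are strong.

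The conclusion that the scale will be overfitted needs a further premise, that all items are fitted or screened on the outcome without shrinkage, and the protocol says nothing of the kind. The modelling method is a gap that commonly falls to the SAP and that an analyst can fill sensibly. Trimming the list in the protocol would gain little for height and weight, and a fixed parameter cap is a trade-off against penalising the full set. The 300 later patients, with 60 to 150 events at the same rates (300 × 0.20 and 300 × 0.50), would give an honest estimate of performance, provided the calibration slope is reported there.

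This rests on one parameter per item, known nodal status in all 500, and R² values that are assumptions.

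### Section IV feeds a 25-item list from records of operated patients into a preoperative scale without limiting scored values to those available before the operation

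*Protocol*

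**What the plan says.** The Purpose section sets the aim: "To create a quantitative rating scale for preoperative prediction of the need for lymph node dissection in patients with thyroid cancer". The Background says that patients will be scored on "a variety of factors prior to surgery, to be able to more accurately predict whether a patient does have lymph node metastasis", and the same sentence goes on to whether prophylactic dissection is needed.

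Section IV (Observation indicators) lists what is collected under five topical headings. Two of them state their timing: the ultrasound group and the laboratory group ("Preoperative laboratory tests: TSH, TPOAb, TgAb, and blood calcium"). Three do not:

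- Basic information ends with "BMI and whether lymph node dissection was performed during previous surgery".
- The tumour group reads "Tumor primary foci: unilateral/bilateral tumor, tumor diameter size, tumor focality, tumor invasion, and cases suggesting lymph node metastasis".
- The genetic group reads "Genetic test results: TERT gene polymorphism (C250T), TERT gene polymorphism (C228T), NRAS gene polymorphism (Q61R), B-raf gene mutation".

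The last paragraph then uses the list as a whole. For development: "The above data were collected from the medical records of previous patients to create a quantitative rating scale". For validation: "then new patients were evaluated using the scale and the above data information was collected from the new patients for comparison and validation". The development set is 500 patients operated on from 2021 to 2023; the validation set is 300 later admissions. No item is named as outcome or as predictor, and none is set aside from scoring.

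**The concern.** A preoperative score can use only what is known before the operation. The 500 development records belong to patients whose operation is over, so they can hold operative and specimen findings beside the preoperative ones. Section IV gives the person abstracting them no rule for choosing between the two.

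Two separate problems could follow.

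- **Outcome or surgical decision in the score.** For the 500, the dissection item most naturally refers to the operation that brought them into the study, which is the decision the scale is meant to inform. If the metastasis item is a pathology result, scoring it means scoring what is to be predicted.
- **Source and availability.** Laterality, diameter, focality, invasion and the four gene results are legitimate predictors. If they are read from operative or specimen records, however, they may be unavailable, or have different values, when the scale is used. This is not outcome leakage, but it can still make accuracy look better than it will be in use.

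Validation would normally expose such a fault. Here the same list is collected again and no scoring time relative to surgery is given, so the fault could recur in the 300 and go unseen.

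**Working it through.** The plan gives no figure to reproduce on this point. The check is an item count of Section IV, followed by a comparison of its wording with the stated aim.

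**Step 1. Count by heading.**

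| Heading in Section IV | Items | Labelled preoperative? |
|---|---|---|
| Basic information | 6 | No |
| Tumour primary foci | 5 | No |
| Ultrasound | 6 | Yes |
| Laboratory tests | 4 | Yes |
| Genetic tests | 4 | No |
| Total | 6 + 5 + 6 + 4 + 4 = 25 | |

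**Step 2. Regroup by what is known about timing.**

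| Group | Items | Share of 25 |
|---|---|---|
| Labelled preoperative (ultrasound 6 + laboratory 4) | 10 | 10/25 = 40% |
| Knowable before surgery by nature (sex, age, height, weight, BMI) | 5 | 5/25 = 20% |
| Dissection item and metastasis item | 2 | 2/25 = 8% |
| No stated preoperative source (4 tumour + 4 genetic) | 8 | 8/25 = 32% |

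Check: 10 + 5 + 2 + 8 = 25. If the metastasis item is counted with the tumour group instead, the unlabelled group is 9 and the dissection item stands alone.

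**Step 3. Set the texts side by side.** The Background limits scoring to factors before surgery. Section IV's closing paragraph sends the whole list into building the scale, without exception. The list gives ultrasound its own preoperative heading and places diameter, laterality, focality and invasion elsewhere, so their source is left open. Enlarged neck nodes already appear under ultrasound, so the metastasis item under tumour foci is not plainly the same imaging sign. The exclusion criteria cite both preoperative puncture pathology and postoperative pathology, so both kinds of record are expected to exist.

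**Step 4. Consequence under each reading.**

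| How the list is used | Consequence |
|---|---|
| The 2 items are not scored and the 8 are preoperative | No bias from this source |
| Dissection performed is scored | The score contains the decision it should inform |
| Metastasis item is pathology and is scored | The score contains the outcome |
| Metastasis item is a preoperative imaging sign | A legitimate predictor |
| Any of the 8 comes from operative or specimen records | The value may not be available at use; accuracy may be overstated |

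The document does not choose among these rows, so no bias can be calculated.

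**The case against.** The strongest reply is that the Background already ties scoring to preoperative factors, and that Section IV is a collection list and not a model. The outcome has to be collected to build any scale, and dissection status has an ordinary descriptive use, since it shows in whom nodal pathology could exist. Roles may be assigned in a statistical analysis plan that is not shown. Preoperative puncture is contemplated, so the gene results could come from it.

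Much of this stands. Collecting the outcome is not an error, the general intent is clear, and assigning predictor and outcome roles is commonly left to the analysis plan. What does not fall away is source and timing. The Background's intent is not carried into Section IV, whose own wording puts the whole list into the scale. If an abstractor records a diameter without saying whether it came from ultrasound or specimen, a later analysis cannot recover the difference.

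Three stronger readings are tempting, and the document does not support them.

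- *The eight items are postoperative.* The protocol does not say so; it omits the label.
- *The Background and the Purpose contradict each other on the outcome.* They do not: the Background sentence names both metastasis and whether dissection is needed, and the Purpose repeats the second.
- *The harm can be sized by contrasting metastasis with dissection performed.* The protocol never makes dissection performed the target; it speaks of need. The hospital's own dissection rate is not given either.

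**Conclusion.** The point holds as a fault of wording that governs data collection. Section IV, as written, allows operative or specimen values into a scale that the protocol describes as preoperative, and the validation step is not timed so as to reveal it. It concerns 2 of 25 items (8%) that are a surgical event or a possible outcome, and 8 of 25 (32%) with no stated preoperative source. These are shares of the list, not measures of bias. The size of any bias is unknown, and it is nil if the two items are left unscored and the eight are taken before surgery.

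The conclusion assumes that, for the 500, the previous surgery in the dissection item is the operation under study, which is the natural reading of how they were selected. It should be settled before abstraction, because the source of a value cannot be restored afterwards if it was not recorded.

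**What to change.** Amend the last paragraph of Section IV so that:

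1. Only values available before the operation are scored. Source and date are recorded for the four tumour and four genetic items, under the same rule in the 500 and the 300.
2. Dissection performed is collected but is not a scored item. The metastasis item is designated either the outcome, from pathology, or a preoperative sign, from imaging, and not both.
3. The score of each of the 300 is recorded before the operation and before pathology is known.

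The cost is a few sentences of protocol text and source and date fields on the data form. There will be more missing values, most of all for gene results that exist only from the specimen. Reported accuracy will probably be lower, but it will describe the scale as it would be used.
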